2. carrying your school bag to school

3. sitting on a school chair for a 45 min. lesson

4. standing in a queue for 10 min.

5. sitting up in bed from a lying position

6. bending down to put your socks on

7. standing up from an armchair at home

8. running fast to catch a bus

9. sport activities at school

11) Tired during the day (42, 45).

Sample-size

The sample-size in this study was determined using the two following rationales: 1) a sample-size large enough to test and replicate the analyses from previous studies on. Given the prior odds (0.5, 1, 2) of follow-up MSK pain for patients, using estimates for the prognostic factors female sex, high disability index, multisite pain, and maximum HFAQ from our systematic review(14). We gained an estimate of P-values according to sample size, for all factors individually (Appendix 8). Sample size of 500 patients, would result in an estimate of P-values below 0.05 for all prognostic factors and 2) investigate a range of new prognostic factors related to the sparsely investigated ethnicity and socioeconomic status. As no one has yet tested any of these potential important prognostic factors, and never in a general practice setting, we decided on 500 subjects. The 500 subjects was decided based on 250 cases (we assume 50% will continue to experience pain at our primary follow-up time) giving approximately 125 cases per prognostic factor (500/number of prognostic factors). The results from this analysis will be considered as explorative as no studies have previously been conducted in a general practice setting. Again, assuming 50% has pain at follow-up and 20 events for each to be tested factor are needed. The model should allow for 10-15 variables in a multivariable logistic regression analysis. This would lead to a sample size of 480. Assumed, 5% is lost to follow-up and we have a sample-size of 504 included participants. Given the high prevalence of MSK pain at follow-up, this sample-size is feasible to include.

Questionnaires

We use three questionnaires in data collection of patient and parent characteristics: participant baseline questionnaire (Part-Quest-base) (Appendix 1), participant follow-up questionnaire (Part-Quest-follow-up) (Appendix 2), and the parent questionnaire (Pare-Quest) (Appendix 3).

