Appendix 1: Participant Baseline Questionnaire (Part-Quest-baseline)

11. How long have you had your current pain? (50) _____
12. What is the cause for your current MSK pain (ex. a fall, a hit or other)? (If you are familiar with it) (50) _____
13. How long does a pain episode usually last (40)?
 Less than 3 hours
 Less than 24h
 1-7 days
 More than 7 days
14. How often do you have a pain episode?(51)
 At least once a week
 Less than once a week
15. How often do you feel nervous?(52)
 Often/sometimes Seldom/never
16. Which zipcode(s) do you live in? _____
17. If not born in Denmark, in which country were you born and how long have you lived in Denmark?
 Country of birth _____ Months/years lived in Denmark _____
18. What do you feel the most as? (53) Please answer this question, no matter country of birth.
 Danish
 Danish with foreign background
 Foreigner
 I don't know
19. How large a part of your friends have immigrant background/not born in Denmark? (53) Mark one.
 None Almost none Almost all All
20. Outside school hours, how many hours a day do you spend watching TV/tablet/mobile phone/computer or do other activities when mostly sitting down(39)? _____ hours/day
- 
-  19. How much do you sleep on average per night(43)?
 7 hours or less
 8-10h
 More than 10 hours
21. Are you physical active besides school hours? (10) 
 Yes
If yes, how many times per week are you physical active besides mandatory physical education during school hours? _____
 No
22. How often do you drink alcohol? (39, 54)
 More than once a month
 Approximately once a month
 Less than once a month
 I have only had alcohol one time
 I have never had alcohol
23. Do you smoke cigarettes(55)?
 Yes, less than 1 a day
 Yes, 1-4 a day
 Yes, 5-9 a day
 Yes, more than 9 a day
 No, I don't smoke cigarettes
24. How many siblings (including non-biological) do you have? _____
–What number are you in your group of siblings? _____
- 

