Appendix 2: Participant follow-up Questionnaire (Part-Quest-Follow-up)

11. What is the cause for your current MSK pain (ex. a fall, a hit or other)? (If you are familiar with it)

12. How long does a pain episode usually last?

- Less than 3 hours
- Less than 24 hours
- 1-7 days
- Longer than 7 days

13. How often do you have a pain episode?

- I don't have breaks from the pain
- At least once a week
- Less than once a week

14. How often do you feel nervous?

- Often/sometimes
- Seldom/never

15. How large a part of your friends have immigrant background?

- None
- Almost none
- Almost all
- All

16. Outside school hours, how many hours a day do you spend watching TV/tablet/mobile phone/computer or do other activities when mostly sitting down? _____ hours/day

17. Are you physical active besides school hours?

- Yes - how many times per week are you physical active besides mandatory physical education during school hours? _____
- No

18. Do you smoke cigarettes?

- Yes - how many cigarettes a day? less than 1 1-4 5-9 more than 9
- No

19. Do you expect to be pain free in the future?

- Yes, in the near future
- Yes, in the long term future
- No

20. Why did you come to your doctor today? You may choose more than one answer with circles.

- I want my pain to stop
- I am worried about the cause of my pain
- My family made me come
- I have a personal problem
- Because of my pain, I can't use my body as I used to

21. Do you expect your doctor to give you medication for your pain?

- Yes, I would like that
- No, I don't think so
- I don't know

22. If you have a job, what do you do _____ and how many hours do you work on a weekly basis? _____

In the following last questions mark "x" in either yes or no

Does your pain make any of the following activities difficult?	Yes	No
-reaching up to get a book from a high shelf		

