Appendix 3: Parent Questionnaire (Pare-Quest)

1. What is your relation to the child? (58)
 - Mother
 - Father
 - Other
2. What is your biological relation to your child?
 - Biological parent
 - Stepparent
 - Adoptive parent
3. How old are you? _____
4. What are your living arrangements with your child?
 - My child does not live with me
 - My child lives with me part time
 - my child lives with me full time
5. What is your relationship status with your child's other parent?
 - I am married to my child's other parent
 - I live with my child's other parent outside marriage
 - I am separated/divorced from my child's other parent/we don't live together
6. Where were you born? (58)
 - Denmark
 - Other – where? _____ and how many months/years have you lived in Denmark? _____
7. Do you smoke cigarettes? yes / no
8. Have you experienced chronic pain of more than 6 months, associated with arthritis, migraine, cancer, stomach ulcers or in your muscles, bones or tendons? (59) yes / no
9. Has one or more of your child's siblings had pain in their muscle, joint, bone or tendon? yes / no
10. Do you take pain killers, when you feel pain? yes / no
11. What do you feel the most as?
 - Danish
 - Danish with foreign background
 - Foreigner
12. Are you religious?
 - Yes
 - No
 - I don't know
13. What is your profession? _____ and how many hours do you work on a weekly basis? _____
14. How many years of education have you had? (58)
 - < 10 years
 - High school or other 10-12 years
 - Bachelor or other 13-15 years
 - University or other 15-17 years_
 - PhD or other > 18 years
15. What is the total income of your household b. tax? (58)
 - <200.000DKR
 - 200.000-350.000DKR
 - 350.000-750.000DKR
 - >750.000DKR
16. Has a health care professional ever given your child the diagnosis hypermobility? yes / no
17. Does your child have a measured/known vitamin D insufficiency? yes / no
18. Has your child been vaccinated (once or more) against HPV (Human Papilloma Virus)? yes / no
19. Has your child received physiotherapy in the past 6 months for the current pain condition? yes / no
20. Do you believe your child feels anxious or depressed? yes / no
21. Do you believe your child has low self-esteem? yes / no
22. Have you accepted your child's pain condition? yes / no
23. Would you like the general practitioner to give your child pain medication? yes / no
24. Why did your child visit the doctor with his/her pain condition? You may circle more than one answer.
 - For pain relief

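### Two ethnicity and socioeconomic items have faulty answer scales: the friends item has no middle option, and the parent education bands overlap at 15 years and leave out 18

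*Protocol*

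**What the plan says.** The Sample-size section gives two reasons for the study size. The second is to "investigate a range of new prognostic factors related to the sparsely investigated ethnicity and socioeconomic status". The section on the literature search also says that ethnicity, race, parental income and residence were thinly covered in the team's review and will be studied here. The Questionnaires section treats the factors collected on the forms as candidate prognostic factors.

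The items in question are these.

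- **Friends, baseline (Appendix 1, item 19).** The child is asked "How large a part of your friends have immigrant background/not born in Denmark" and marks one of four options: "None Almost none Almost all All".
- **Friends, follow-up (Appendix 2, item 15).** The question is "How large a part of your friends have immigrant background", without the part about not being born in Denmark. The same four options are listed on separate lines.
- **Parent education (Appendix 3, item 14).** The parent is asked "How many years of education have you had". After bands for under 10 and 10-12 years, the last three are "Bachelor or other 13-15 years", "University or other 15-17 years" and "PhD or other > 18 years".
- **Household income (Appendix 3, item 15).** The bands are below 200.000, 200.000-350.000, 350.000-750.000 and above 750.000 DKR.

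**The concern.** A closed item measures an exposure only if every respondent has exactly one true box. The friends item fails this across the whole middle of its range. A child with a quarter, half or two thirds of friends of immigrant background has no true answer and no option for not knowing. The education item fails at two points on its upper half.

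The answer given on the form is the only record of the exposure. If a mixed friend group is recorded as almost none or almost all, or left blank, the analyst cannot tell afterwards what the child meant. A finding of no association for that item could then reflect the boxes and not the factor. That the analysis is exploratory does not remove the problem, because an exploratory result is useful only if the exposure was measured.

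A smaller point is that the two forms do not define immigrant background in the same way. A Danish-born friend of immigrant descent may be counted differently on the two forms, and the Questionnaires section itself separates immigrants from a descendant.

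**Working it through.** **1. Friends item.** The options at baseline and follow-up are identical: none, almost none, almost all, all. Nothing lies between the second and third. Because the two forms agree, and the follow-up form lists the options line by line, a middle option lost in reading the PDF is an unlikely explanation.

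**2. Education.** Each whole year from 8 to 21 was set against the five printed bands.

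| Years | Bands that fit |
|---|---|
| 8, 9 | <10 |
| 10, 11, 12 | 10-12 |
| 13, 14 | 13-15 |
| **15** | **13-15 and 15-17** |
| 16, 17 | 15-17 |
| **18** | **none** |
| 19, 20, 21 | >18 |

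So 15 years has two boxes, 18 years has none, and every other year has exactly one.

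**3. Income.** 350.000 closes one band and opens the next, so it has two boxes. 200.000 belongs only to the second band, because the first is strictly below it. 750.000 belongs only to the third, because the last is strictly above it. The fault is confined to one exact value.

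**4. The plan's sample size.** Inputs from the Sample-size section are 20 events per factor, a 50% outcome rate, 10-15 variables and 5% loss. The formula is variables × 20 / 0.5.

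- 10 variables: 10 × 20 / 0.5 = 400
- 12 variables: 12 × 20 / 0.5 = 480, the stated figure
- 15 variables: 15 × 20 / 0.5 = 600
- Adding 5%: 480 × 1.05 = 504, the stated figure

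None of these inputs depends on the answer boxes, so N does not change.

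**5. How many children could be affected.** The documents give no share with mixed friend groups. Assuming 10% to 30%: 0.10 × 500 = 50 and 0.30 × 500 = 150 children without a correct box. This is a range on an assumed input, not an estimate.

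**6. What misclassification could do, for illustration only.** Assume a binary factor with prevalence 0.5, outcome rate 50%, N = 480, a true odds ratio of 1.78 (borrowed from the sex row of Appendix 5) and a fraction m misplaced equally in both directions and independently of the outcome. Then the true outcome odds are √1.78 = 1.334 and its inverse in the two groups, so p1 = 0.572 and p0 = 0.428. Among those recorded as exposed, q1 = (1 − m)p1 + m·p0, and by symmetry q0 = 1 − q1. The observed odds ratio is (q1/q0)². For m = 0.10, q1 = 0.9 × 0.572 + 0.1 × 0.428 = 0.557 and the observed odds ratio is 1.58.

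| m | Observed odds ratio | Power (two proportions) |
|---|---|---|
| 0 | 1.78 | 88% |
| 0.05 | 1.68 | 81% |
| 0.10 | 1.58 | 71% |
| 0.20 | 1.41 | 47% |

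This shows one possible mechanism. The documents do not establish that the error here would take this form.

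**The case against.** The other side has several good points.

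- **Most related items are sound.** Zipcode, country of birth with time in Denmark, and self-identity (Appendix 1, items 16-18), and parental birthplace, self-identity and profession (Appendix 3, items 6, 11 and 13) do not have these faults. A reader might infer that the new factors as a group are misclassified. The documents do not support that; the fault lies in two items, plus one income value. This stands.
- **The direction of bias is not known.** A reader might infer that associations will be pulled towards no effect. That needs errors that are random and unrelated to outcome, which nothing in the documents shows. Children may choose systematically, or leave the item blank, which gives missing data. With four levels, even error unrelated to the outcome need not shrink every contrast. This stands.
- **No count per side follows.** One might split the 50 to 150 children evenly between the two ends. But that number would include children with some or most friends of immigrant background, who have a nearer end, and the documents say nothing about how they would choose. This stands.
- **Education can be partly rescued.** Parents can answer by degree label. Merging 13-15 with 15-17 removes the overlap, and merging everything from 13 years up also absorbs 18 years. What remains is under 10, 10-12, and 13 or more. Blank answers stay blank, and any gradient within higher education is lost.
- **The follow-up form matters less.** The objective uses exposures collected at recruitment, so the follow-up friends item does not supply the prognostic exposure. This stands, and the baseline item carries the point.
- **Exploratory status and piloting.** Results are declared exploratory, and the forms are to be pilot tested. Piloting might reveal the gap, but the protocol states no revision of these boxes.

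None of this supplies a correct box for a child with a mixed friend group.

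**Conclusion.** The point holds for two items. The friends item has no option between almost none and almost all, and the lost category cannot be recovered in analysis. Parent education is ambiguous at 15 years and empty at 18, and merging recovers only a coarser gradient. Income overlaps at exactly 350.000, which is trivial.

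The size cannot be fixed from the documents. The 50 to 150 of 500 rests wholly on an assumed 10% to 30% with mixed friend groups, and the power figures rest on an assumed error mechanism. The sample size, the primary outcome and the remaining ethnicity and socioeconomic items are untouched. This is a defect that should be corrected because the items serve a stated purpose of the study and the correction is cheap; it does not undermine the study as a whole.

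**What to change.** **Before the forms are printed and translated:**

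- Friends item, in both Appendix 1 (item 19) and Appendix 2 (item 15): add at least one middle category, such as *About half*, or preferably *Some*, *About half* and *Most*. Use the same definition of immigrant background in both forms.
- Education (Appendix 3, item 14): ask for years as a number, or make the bands exclusive and exhaustive, for example <10, 10-12, 13-15, 16-17, and 18 or more. If the degree labels are kept, check that they agree with the bands.
- Income (Appendix 3, item 15): assign 350.000 to one band only. The other limits need no change.

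The cost is rewording of answer boxes and the matching edits to the translations. The downside is that the friends item would no longer match its cited source exactly. Its four levels could not be fully rebuilt either, because a child answering *About half* belongs to neither neighbouring level.

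**If data are already collected:** merge the affected education bands, state how blank friends answers are handled, and report the limitation when interpreting a null result for these items.

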Appendix 5: Sample size

Sample size calculations for prognostic factors of adolescents with musculoskeletal (MSK) pain

[name]

November 23, 2017

Introduction

We want to identify prognostic factors for adolescents with musculoskeletal (MSK) pain.

DISCLAIMER

These calculations are provisional and exploratory. Many assumptions are made and they may turn out not to hold. Please use with care.

Prognostic factors

These factors are believed to be prognostic for still having MSK pain at follow-up:

- Female sex compared to male sex OR 1.78 (1.18-2.69)
 - Study id 12, study id 2 comparable
- Sleeping < 7h/day vs. 8-9 h/day OR 1.68 (1.05-2.68)
 - Study id 17, females, 2 years follow-up

It is assumed that the confidence intervals are 95% and that the prognostic factors are independent.

Power calculations

The column **frac1** refers to the fraction of the population with this prognostic factor **Level1**.

The column **OR** refers to the OR for having prognostic factor at **Level1** (instead of **Level2**).

Type	Level1	Level2	frac1	OR	OR_L	OR_U	logOR
Sex	Female	Male	0.5	1.78	1.18	2.69	0.577
Sleep	Problematic	OK	0.2	1.68	1.05	2.68	0.519

It is natural to assume that a log odds ratio follow a normal distribution. The standard deviation is approximately $(\log(\text{OR}_U) - \log(\text{OR}_L))/4$.

We now assume that we have n individuals at baseline. Each individual will have a prognostic factor or not (according to **frac**). For example for $n = 10$:

Sex	Sleep
Male	OK
Male	OK

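### The baseline sleep item does not match the sleep contrast in Appendix 5, has no box for averages between 7 and 8 hours, and records no hours from which the contrast could be rebuilt

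*Protocol*

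**What the plan says.** Appendix 1 (Participant Baseline Questionnaire) asks "How much do you sleep on average per night(43". The lowest box is "7 hours or less", the middle one covers 8 to 10 hours, and the highest is "More than 10 hours". The item has no space to write a number of hours. The follow-up form (Appendix 2) asks whether pain makes it hard to fall asleep, but not how long the participant sleeps, so baseline is the only time sleep duration is collected.

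Appendix 5 (Sample size) works through two prognostic factors, sex and sleep. Sleep is given as "Sleeping < 7h/day vs. 8-9 h/day OR 1.68 (1.05-2.68", with the source noted as "Study id 17, females, 2 years follow-up". The row that enters the simulation is "Sleep Problematic OK 0.2 1.68 1.05 2.68 0.519", that is, 20% of the population at the exposed level. The appendix carries its own caution: "These calculations are provisional and exploratory".

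The Sample-size section of the main text gives as its first rationale a cohort "large enough to test and replicate the analyses from previous studies on". The factors it then names for that rationale are female sex, disability index, multisite pain and the HFAQ score. Sleep is not among them.

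**The concern.** Sleep is one of only two factors in the one worked calculation the protocol shows, and the form cannot produce the groups that calculation describes. Participants who sleep exactly 7 hours belong to neither side of the Appendix 5 contrast, yet the form counts them as short sleepers. Those who sleep more than 9 and up to 10 hours are outside the stated reference but fall in the comparison box. A respondent whose average lies between 7 and 8 hours has no correct answer and must round or leave the item blank.

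Because only the box is stored, no analysis plan can repair this later. The sleep OR from this cohort will describe a different contrast from the one in Appendix 5, and readers who compare the two will not be comparing like with like.

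**Working it through.** **1. The plan's own figures.** The events-per-variable argument assumes 50% with pain at follow-up and 20 events per factor. With 12 variables (inside the stated 10-15), 12 × 20 / 0.50 = 480, and 480 × 1.05 = 504. Both stated figures reproduce, and neither uses the sleep item. In Appendix 5, ln(1.68) = 0.519, as printed.

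**2. Definitions side by side.**

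| | Appendix 5 | Appendix 1 |
|---|---|---|
| Short sleep | under 7 h | 7 h or less |
| Comparison | 8-9 h | 8-10 h |
| Exactly 7 h | in neither group | short sleep |
| Between 7 and 8 h | in neither group | no box |
| Above 9 and up to 10 h | in neither group | comparison |

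**3. Power on Appendix 5's own sleep inputs.** Take N = 500, 100 exposed and 400 not, sex split 50:50 with OR 1.78, and baseline odds of 1. The risk in the unexposed is 0.5 × 0.500 + 0.5 × (1.78/2.78) = 0.570. The risk in the exposed is 0.5 × (1.68/2.68) + 0.5 × (2.990/3.990) = 0.688. Two-sided 5% power is about 58%. At baseline odds of 1/2 and 2 it is about 62% and 45%. The sleep contrast is weakly powered before the boxes are considered.

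**4. What the lowest box could do.** The documents do not give the share sleeping exactly 7 hours or the risk at 7 hours, so these are assumptions. I take 500 × 0.95 = 475 analysed, a reference risk of 0.50, 20% under 7 hours at OR 1.68 (risk 1.68/2.68 = 0.627), and a further 20% at exactly 7 hours. The box then holds 40% (190) and everyone else is the comparison (285).

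Formulas: pooled risk p = weighted mean of the two risks; pooled OR = [p/(1−p)] / 1; SE(log OR) = √[1/(n₁p(1−p)) + 1/(n₀ × 0.25)]; power = Φ(log OR/SE − 1.96).

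- Contrast as planned, no 7-hour sleepers added (95 against 380): SE = √(1/22.2 + 1/95) = 0.236; 0.519/0.236 = 2.20; power about 0.60. With the 20% at 7 hours left out (95 against 285), power is about 0.57.
- 7 hours at reference risk: p = (0.627 + 0.500)/2 = 0.563; OR 1.29; SE 0.188; 0.255/0.188 = 1.36; power about 0.27.
- 7 hours at OR 1.3 (risk 0.565): p = 0.596; OR 1.48; SE 0.189; 0.389/0.189 = 2.05; power about 0.54.
- 7 hours at the full OR 1.68: p = 0.627; OR 1.68; SE 0.191; 0.519/0.191 = 2.71; power about 0.77.

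**5. Range.** With 10-30% of the sample at 7 hours, the pooled OR runs from 1.23 (30% at reference risk) to 1.54 (10% at OR 1.3). If 7 hours carries the full 1.68, the OR is unchanged and power is about 0.72-0.79. Widening the comparison box to 10 hours has a further effect that the documents do not allow one to size.

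**The case against.** The strongest reply is that little hangs on this. The Sample-size section names four other factors for its P-value rationale, and the final number rests on events per variable. A reader might infer that the mismatch undermines the sample size. The documents do not support that: no stated number changes, and the calculation that uses sleep is labelled provisional.

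A reader might also infer that the exposed group is necessarily diluted and the sleep effect weakened. That holds only if risk at exactly 7 hours is lower than below 7 hours. It is plausible, but the protocol does not show it, and at equal risk the larger group raises power.

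Nor can the boxes be blamed for preventing an exact replication. The source estimate comes from females followed for 2 years, while this cohort takes both sexes from general practice with a 6-month primary follow-up. A null sleep result would be hard to read as a failed replication whatever the form said.

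Finally, the contrast in Appendix 5 itself leaves 7 to 8 hours unassigned, and its simulation treats everyone outside the exposed 20% as the reference level.

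All of this stands, and it limits the consequence. It does not remove the fault in the form: the boxes are not exhaustive, they differ from the only sleep definition the protocol gives, and the answers cannot be regrouped afterwards.

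**Conclusion.** The point holds as a minor fault of data capture. The mismatch of cut-points and the missing box can be read directly from the two appendices and need no assumption. The effect on the sleep estimate cannot be fixed from the documents. Under the assumptions shown (475 analysed, 50% reference risk, 20% under 7 hours, a further 20% at 7 hours), power ranges from about 0.27 to about 0.77, against about 0.60 as planned, so even the direction is unknown. The recruitment target is unaffected, and sleep is one exploratory candidate factor, not part of the primary outcome.

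**What to change.** Replace the three boxes with a blank for average hours of sleep per night. The baseline form already uses this format for daily screen time. Everyone can then answer, and the contrast of under 7 against 8-9 hours, or any other grouping, can be derived. How sleep enters the multivariable model is a matter for the analysis plan and need not be settled here.

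The cost is one reworded item on the baseline form and in its translations, with possibly a few more blanks or less precise answers from the youngest children. The change helps only participants who complete the revised form, since boxes already ticked cannot be converted back to hours.
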